7.3 Questionnaire outcomes

Total and individual questionnaire related outcomes for

- 1) Continual sore mouth or throat
- 2) Oral thrush
- 3) Hoarse voice

* Calculated as average number of puffs per day over the year multiplied by strength (in µg);

[†] See appendix 1 for definitions

i.e. $\frac{\text{Number of inhalers} \times \text{doses per inhaler}}{365} * \text{strength}$

- 4) Bruising
- 5) Abnormal weight gain
- 6) Cough

As an exploratory outcome, the prescribed ICS dose at index dose will be considered to create the subgroups of step down patients for the Volumatic and Aerochamber spacers.

7.4 Database outcomes

Total and individual database outcomes including Read code diagnosis for

- 1) Oral thrush
- 2) Rash
- 3) Oedema/swelling
- 4) Adrenal suppression diagnosis
- 5) Osteoporosis/osteopenia
- 6) Anxiety/depression
- 7) Cataracts
- 8) Glaucoma

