3.0 Background

Asthma is considered a heterogeneous obstructive lung disease caused by an inappropriate inflammatory reaction in the airways. Increased mucus production and bronchospasm can lead to exacerbations and significant mortality. Narrowed airways can result in reduced quality of everyday living – the Royal College of Physicians three questions surveys whether asthma is controlled by asking the patient whether they have nocturnal disturbances, whether asthma limits activity, and whether they suffer from any daytime symptoms. Treatment of asthma is centered around the use of inhaled corticosteroids, which are recommended in all but the mildest patients with asthma¹. The latest GINA guidelines recommend patients who require their reliever more than once a fortnight be prescribed inhaled corticosteroids¹. Reducing the inflammatory response not only helps control the disease, prevents exacerbations and reduces the daily symptoms, but also might help to reduce any chronic changes that occur as a result of long term inflammation.

However, the use of corticosteroids can cause significant side effects, especially when prescribed to young children or when higher doses are required. Inhaled corticosteroids are dispensed at significantly lower doses than oral corticosteroids, significantly reducing the risk of glucocorticoid side effects compared to oral therapy ²(Table 1).

System Class	Adverse Reaction	Frequency
Infections	Oral thrush	Very common
Immune system	Rash, urticarial, pruritus, erythema	Uncommon
	Oedema	Very Rare
Endocrine	Adrenal suppression, bone density reduction, growth retardation	Very Rare
Psychiatric disorders	Psychomotor hyperactivity, sleep disorder, depression, anxiety, behavioural disorders	Unknown
Nervous system disorders	Headache	Unknown
Eye disorders	Cataracts, glaucoma	Very Rare
Thoracic disorders	Hoarseness, throat irritation	Common
	Cough, bronchospasm, wheezing, dyspnoea	Very rare
Gastrointestinal	Nausea	Unknown

Table 1: Side effects of non-extrafine beclomethasone dipropionate listed by system ³

Unlike oral therapy, the use of inhaled corticosteroids requires a meaningful delivery of the drug to the lungs, which requires good adherence and a proper inhaler technique from the

patient. Up to 80% of the inhaled drug ends up impacting in the oropharynx and being systemically absorbed, even when good technique is used. Accordingly, spacer devices are suggested to improve drug delivery to the lungs⁴.

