Patient-reported side effects will provide a unique perspective to disease outcomes compared to database Read codes, where bruising for example is seldom reported. An extract of the adult and child questionnaire is shown below (Figure 2 and Figure 3).

Do you experience any of these side effects from your preventer inhaler? Please tick yes or no for each one

	Yes	No		Yes	No
Continual sore mouth/throat			Hoarse voice		
Oral Thrush			Abnormal Weight Gain		
Bruising			Cough		

Figure 2: British Lung Foundation asthma questionnaire extract for adults

Does your child experience any of the following side effects from their preventer inhaler? Please tick Yes or No for each one

	Yes	No		Yes	No
Continual sore mouth or throat			Hoarse voice		
Oral thrush			Abnormal weight gain		
Bruising			Cough		

Figure 3: British Lung Foundation asthma questionnaire extract for children

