4.2 Study objectives

4.2.1 Primary objective

Non-inferiority of non-extrafine beclomethasone dipropionate with Aerochamber[®] spacer compared to non-extrafine beclomethasone dipropionate with Volumatic[®] spacer, in terms of the rate of patient-reported outcomes listed on the British Lung Foundation Questionnaire, ie the incidence of oral thrush or hoarseness.

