4.2.2 Secondary objective

Comparison of database outcomes for non-extrafine beclomethasone dipropionate with Volumatic[®] spacer and non-extrafine beclomethasone dipropionate with Aerochamber[®] spacer in terms of Read codes for adverse reactions to beclomethasone dipropionate over a three-year period.

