7.2 Demographics and baseline variables for database outcomes

- Gender (male/female)

* Calculated as average number of puffs per day over the year multiplied by strength (in µg);
i.e. $\frac{\text{Number of inhalers} \times \text{doses per inhaler}}{365} * \text{strength}$

† See appendix 1 for definitions

- Age of patient (years, at index date)
- Body Mass Index (BMI, at time nearest index date, calculated from height and weight data if available, otherwise taken from practice-recorded BMI value, detailed definition in Appendix 1)
- Smoking status (identified by Read code, closest to index date)
- SABA daily dose calculated in baseline prior to index date*
- Percentage predicted peak flow (peak flow predicted, closest to index date)
- Total cumulative ICS dose
- Total cumulative non-extrafine beclomethasone dipropionate therapy
- Duration of ICS therapy
- Number of exacerbations (ATS/ERS 2015 consensus definition[†]) prior to index date
- Number of oral corticosteroid prescriptions prior to index date
- Number of antibiotic prescriptions for lower respiratory tract infections prior to index date
- History of comorbidities related to asthma:
 - Pneumonia (Read code diagnosis in the year prior to the index date)
 - Diabetes (Read code diagnosis and/or antidiabetic drugs ever prior to the index date)
 - Ischaemic heart disease (Read code diagnosis prior to the index date)
 - Rhinitis (Read code diagnosis, including chronic and allergic rhinitis and prescriptions for nasal steroids prior to index date)
 - Eczema (Read code diagnosis prior to index date)
 - Osteoporosis (Read code diagnosis prior to the index date)
 - Charlson Comorbidity Index (based on Read code diagnoses in the year prior to index date, detailed definition in Appendix 1)

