8.4 Analysis of study outcomes

8.4.1 Primary analysis: Questionnaire based adverse events

Adverse events as total and individual events in the questionnaires will be compared using a conditional Poisson regression model. The model will use empirical standard errors and adjustments will be made for potential baseline confounders.

The adjusted rate ratio with 95% confidence interval will be reported.

Non-inferiority in patient reported adverse events (oral thrush OR hoarseness) will be achieved if the proportion of Clenil/Aerochamber is no more than 13% higher (based on the upper boundary of the 95% confidence interval) than the proportion of patients on Clenil/Volumatic.¹⁴

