8.4.2 Secondary analysis – database outcomes

The total number of adverse events as listed in the Summary of Product characteristics in the outcome period will be compared between treatment groups compared using a conditional

Poisson regression model. The model will use empirical standard errors and adjustments will be made for potential baseline confounders.

The adjusted rate ratio with 95% confidence interval will be reported.

Exploratory analysis – The exacerbation rate and separately the daily SABA dosage for patients during the baseline year who step down ICS at the index date treated with an Aerochamber spacer will be compared to patients prescribed a Volumatic spacer and compared with a Wilcoxon ranked test.

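### The database outcome list in section 7.4 omits hoarseness, one of the two primary-endpoint components, and does not match the total analysed in section 8.4.2

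*Protocol*

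**What the plan says.** The primary objective (protocol section 4.2.1) is stated as "ie the incidence of oral thrush or hoarseness", and section 8.4.1 repeats the pair: "Non-inferiority in patient reported adverse events (oral thrush OR hoarseness". Both components come from the patient questionnaire.

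Table 1 in section 3.0 sets out the side effects of the product by system. Oral thrush is rated very common. The row "Hoarseness, throat irritation" is rated common. No other row reaches either of these two bands.

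The secondary objective (section 4.2.2) compares the spacers "in terms of Read codes for adverse reactions to beclomethasone dipropionate over a three-year period". Section 7.4 sets out what is counted: "Total and individual database outcomes including Read code diagnosis for" oral thrush, rash, oedema/swelling, adrenal suppression, osteoporosis/osteopenia, anxiety/depression, cataracts and glaucoma. Section 8.4.2 describes the analysed quantity differently: "The total number of adverse events as listed in the Summary of Product characteristics in the outcome period".

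On ascertainment, section 3.0 says that patient reports add information "compared to database Read codes, where bruising for example is seldom reported". Some baseline conditions are defined by code plus treatment, for example "Diabetes (Read code diagnosis and/or antidiabetic drugs ever prior to the index date". No treatment-based definition is given for oral thrush as an outcome.

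**The concern.** The database list keeps several reactions that Table 1 calls very rare and drops the only one it calls common, which is also part of the primary endpoint. A patient seen and coded for a hoarse voice during the three outcome years would count as event-free under section 7.4 but as having an event under section 8.4.2. Two analysts working from different sections would build different totals.

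If section 7.4 governs extraction, the secondary comparison cannot show whether routine records point the same way as the questionnaire on the endpoint that decides non-inferiority. Timing also matters. Section 6.3 says that each study receives only the variables needed for its objectives, and section 13.0 schedules extraction for 10 November 2016, shortly after the protocol date of 28 October 2016. An outcome missing from the list may not be supplied.

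**Working it through.** **Step 1. The plan's own figures.** The protocol gives no event rate, power or precision for the database outcomes. Its sample size (section 8.1) concerns the questionnaire comparison. With 293 and 147 patients, a proportion of 0.300, a margin of 0.130 and one-sided alpha of 0.025:

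- SE = sqrt(0.30 × 0.70 × (1/293 + 1/147)) = 0.0463
- Power = Φ(0.130/0.0463 − 1.960) = 0.801

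The stated 80% reproduces and has no bearing on this point.

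**Step 2. Section 7.4 against Table 1.**

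| Table 1 frequency | Items in section 7.4 | Table 1 items not in section 7.4 |
|---|---|---|
| Very common | oral thrush | none |
| Common | none | hoarseness, throat irritation |
| Uncommon | rash | urticaria, pruritus and erythema (not named) |
| Very rare | oedema, adrenal suppression, bone density (as osteoporosis/osteopenia), cataracts, glaucoma | growth retardation; cough, bronchospasm, wheezing, dyspnoea |
| Unknown | anxiety/depression | hyperactivity, sleep and behavioural disorders; headache; nausea |

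The eight items split 1 very common, 0 common, 1 uncommon, 5 very rare, 1 unknown.

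**Step 3. Section 7.4 against section 8.4.2.** Section 8.4.2 counts events listed in the Summary of Product Characteristics. That document is not at hand, so I take Table 1 as the protocol's rendering of it. On that basis section 8.4.2 includes hoarseness and section 7.4 does not.

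**Step 4. The mock tables in section 15.2.2.** By their printed captions, Tables 19 to 25 and Table 27 have no row for hoarseness, and none for oedema although section 7.4 lists it. Table 26 (under 16 years, higher dose) sits in the same section but carries the questionnaire rows, including hoarse voice. The mock tables therefore do not settle which list is meant.

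**Step 5. How much is missed.** Take local reactions as thrush plus hoarseness. Let t be the share that is thrush and s the probability that a thrush episode is coded. With hoarseness uncounted, the share captured is t × s. Neither input is in the protocol, so both ranges are assumptions.

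| t | s = 0.2 | s = 0.5 | s = 0.8 | s = 1.0 |
|---|---|---|---|---|
| 0.25 | 5% | 12.5% | 20% | 25% |
| 0.50 | 10% | 25% | 40% | 50% |
| 0.75 | 15% | 37.5% | 60% | 75% |

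The result runs from 5% to 75%, on both sides of one half.

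**Step 6. Code-only thrush.** Assume that a fraction c of thrush episodes is coded, equal in both groups and with no false positives. The rate ratio is then unbiased and only precision falls. The variance of the log rate ratio scales roughly as 1/c, so the interval on the log scale widens by sqrt(1/c): sqrt(1/0.7) = 1.20 at c = 0.7, and sqrt(1/0.3) = 1.83 at c = 0.3. These values of c are also assumptions.

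**The case against.** The strongest reply is that section 8.4.2, read literally, already brings hoarseness into the analysed total; that the word introducing the list in section 7.4 can be read as non-exhaustive; and that code lists are commonly settled in an analysis plan that is not shown. The secondary objective also never claims to corroborate the primary one. The protocol knows that Read codes under-record some effects, and it uses the questionnaire, which asks about hoarse voice (section 7.3), for the primary analysis.

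Much of this stands and sets the scale: the matter is confined to the secondary objective. It does not remove the mismatch. If section 8.4.2 is right, sections 7.4 and 15.2.2 are wrong, and a conflict over which events count belongs in the protocol.

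A reader might infer four stronger things that the documents do not support:

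- **That the database misses most local reactions.** Step 5 shows that this depends on two unknowns. Likewise, hoarseness is one of two endpoint components, not half of the events.
- **That the listed conditions have little to do with spacer deposition.** Section 3.0 says that drug deposited in the oropharynx is also systemically absorbed, so systemic reactions belong to the rationale.
- **That the list is mostly adult disease and so empty for under-16s.** Thrush, rash, oedema, adrenal suppression and anxiety/depression, five of the eight, are not confined to adults.
- **That code-only thrush is an error.** Adding antifungal prescriptions raises sensitivity and lowers specificity. False positives at equal rates in both groups would pull the ratio toward 1, which is unwelcome in a safety comparison. The diabetes and rhinitis precedents are baseline covariates, not outcomes.

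**Conclusion.** The omission is a matter of record. Section 7.4 leaves out a component of the primary endpoint that is also the only reaction Table 1 rates common, and sections 7.4 and 8.4.2 define different totals. As section 7.4 is written, hoarseness captured is nil and no database counterpart to the primary endpoint can be formed.

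The conflict with section 8.4.2 rests on one assumption, that Table 1 reflects the Summary of Product Characteristics. The number of events lost cannot be stated from the protocol. The primary questionnaire analysis is unaffected. This is an inexpensive improvement to the secondary comparison, worth making before extraction.

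**What to change.** Before data extraction:

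1. Add an item to section 7.4, and a matching row to the database mock tables: hoarseness/dysphonia or throat irritation (Read code). Keep the hoarseness codes separable from the throat-irritation codes.
2. Report thrush or hoarseness by Read code in the outcome period as a database composite, the counterpart of the primary endpoint.
3. Replace the questionnaire rows in mock Table 26 with the database rows, and add the missing oedema row throughout section 15.2.2.
4. Reconcile the rest of section 7.4 with section 8.4.2 and Table 1. State for each Table 1 reaction whether it counts, and have section 8.4.2 refer to the resulting list. Cover growth retardation and behavioural/sleep disorders explicitly, because section 4.3 prespecifies an under-16 split of the secondary objective.
5. Keep Read-code thrush as the main definition. Add Read code and/or oral topical antifungal prescription as a sensitivity analysis only.

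The cost is a few extra code lists and one prescription variable. Some antifungal prescriptions will have been issued for other reasons, which is why that definition should not replace the main one.

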7.5 Step down outcomes

- 1) Number of severe exacerbations in baseline year
- 2) Daily average SABA category in baseline year

8.0 Statistical analysis

8.1 Software used and power calculation

The dataset will be analysed using SPSS version 23, SAS version 9.3, Stata SE version 14 (StataCorp, College Station, TX) and Microsoft Office EXCEL 2013, as appropriate.

The study was powered using the occurrence of oral thrush as the representative adverse event. The occurrence of adverse events is 34% based on the oropharyngeal side effects in users of ICS in a real life setting reported in the literature¹³.

The minimum study numbers are based on the following assumption:

When the sample sizes in the groups are 293 and 147, a two-group large-sample normal approximation test of proportions with a one-sided 0.025 significance level will have 80% power to reject the null hypothesis that the test and the standard are not equivalent (the difference in proportions, $p_T - p_S$, is 0.130 or farther from zero in the same direction) in favor of the alternative hypothesis that the proportions in the two groups are equivalent, assuming that the expected difference in proportions is 0.000 and the proportion in the standard group is 0.300.

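### Section 8.1 cites a 34% event rate but computes power at an unexplained 0.300, and ties it to oral thrush while the tested endpoint is thrush or hoarseness; at 34% the stated sample has about 77.5% power, not 80%

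*Protocol*

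**What the plan says.** Section 8.1 gives its inputs in consecutive statements.

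- The event: "The study was powered using the occurrence of oral thrush as the representative adverse event".
- The rate, from a cited source: "The occurrence of adverse events is 34% based on the oropharyngeal side effects in users of ICS in a real life setting".
- The calculation: "a two-group large-sample normal approximation test of proportions with a one-sided 0.025 significance level will have 80% power". This is claimed for groups of 293 and 147. The difference to be excluded "is 0.130 or farther from zero in the same direction", the expected difference is zero, and "the proportion in the standard group is 0.300". The section presents the resulting sizes as minimum numbers.

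The endpoint that is tested is defined elsewhere. The primary objective (section 4.2.1) specifies the incidence of oral thrush or hoarseness. The decision rule in section 8.4.1 begins "Non-inferiority in patient reported adverse events (oral thrush OR hoarseness" and sets the limit at 13%.

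**The concern.** Two things in section 8.1 do not fit together. The rate introduced for the calculation is 34%, but the rate entered is 0.300, with neither a reason nor a source. The event named as the basis for power is oral thrush, but the event tested is a composite that adds hoarseness.

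The direction of the change matters. With an absolute margin and equal rates in both groups, the variance is proportional to p(1 − p), which rises as p moves towards 0.5. Moving from 34% to 30% therefore raises the calculated power.

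The stated 80% is the figure by which readers would judge an inconclusive non-inferiority result, and 293 and 147 are the numbers the study sets itself as a floor. Both should rest on a rate that the protocol can defend for the endpoint it tests.

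**Working it through.** **Inputs, all from section 8.1.** Group sizes 293 and 147; absolute margin 0.130; expected difference 0; one-sided significance level 0.025 (z = 1.960); target power 80% (z = 0.8416); rate 0.300 as used, 0.34 as cited.

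**Formula.** Normal approximation for two independent proportions, unpooled variance, same rate p in both groups:

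SE = √[p(1 − p)(1/293 + 1/147)], with 1/293 + 1/147 = 0.010216

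Power = Φ(0.13/SE − 1.960)

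**Step 1: reproduce the plan's figure at p = 0.300.** SE = √(0.21 × 0.010216) = 0.0463. Then 0.13/0.0463 = 2.807, and Φ(2.807 − 1.960) = Φ(0.847) = 80.1%.

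Solving for the smaller group at 2:1: (1.960 + 0.8416)² × 0.21 × 1.5/0.13² = 146.3, so 147. The larger group is 2 × 146.3 = 292.6, so 293. The stated power and both group sizes are recovered, so this is evidently the method used.

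**Step 2: the same formula at p = 0.34.** SE = √(0.2244 × 0.010216) = 0.0479. Then 0.13/0.0479 = 2.715, and Φ(0.755) = 77.5%.

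**Step 3: numbers needed for 80% at p = 0.34.**
- At 2:1, smaller group: 7.849 × 0.2244 × 1.5/0.0169 = 156.3, so 157, with 314 in the larger. The total is 471 against 440, or 31 more patients.
- At 1:1: 7.849 × 0.2244 × 2/0.0169 = 208.4, so 209 per group. This treats the groups as independent. The plan is a matched, covariate-adjusted conditional model, so it is only an approximation.

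**Step 4: range of rates with 293 and 147.** The values 0.25 and 0.40 are assumptions, chosen to lie on either side of 0.30.

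| Rate in both groups | Power |
|---|---|
| 0.25 (assumed) | 84.4% |
| 0.30 (used in 8.1) | 80.1% |
| 0.34 (cited in 8.1) | 77.5% |
| 0.40 (assumed) | 74.7% |

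The break-even rate follows from p(1 − p) = 0.0169/(7.849 × 0.010216) = 0.2108, which gives p ≈ 0.302. For rates below one half, 80% power therefore holds only if the composite rate is about 0.30 or less.

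**Step 5: other variance methods at p = 0.34.** A Farrington–Manning restricted variance gives 79.7% or 76.3%, depending on which spacer group is the larger, which section 8.1 does not say. A continuity correction gives 74.2%. None reaches 80%. At 0.300 these methods give 82.6% or 78.4%, and 76.9%, so none reproduces the plan's figure as closely as the unpooled formula.

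**The case against.** Several points can fairly be made for the plan.

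- **The calculation is not wrong at its declared inputs.** This stands. It reproduces exactly at 0.300. A reader might infer an arithmetic error, but there is none; the fault lies in unreconciled inputs.
- **34% may not be the rate of the tested composite.** This stands too. Section 8.1 attributes it to oropharyngeal side effects. Section 7.3 also lists continual sore mouth or throat, which could count as oropharyngeal but lies outside the thrush-or-hoarseness endpoint. If the 34% includes such events, the composite could be rarer and 0.300 could be a deliberate reduction. The protocol does not say so. It is therefore tempting, but unsupported, to conclude that the study is underpowered because the composite occurs in 34%.
- **The composite need not exceed 0.30.** Thrush or hoarseness cannot be rarer than thrush alone, but the protocol gives no separate thrush rate, so this bound does not place the composite above 0.30. At an assumed 0.25, power would be about 84%. If 0.300 were meant as the thrush rate, the composite would be at least 0.30 and, up to a rate of 0.70, power would be no more than 80.1%.
- **Thrush is called representative, not the sole event.** The wording is loose, and the rate cited is not presented as thrush-only. It still leaves open which event the 0.300 describes.
- **The effect is small.** It is, at about 2.6 points. A reader might reach a much larger loss by combining this with the 1:1 matching in section 8.3, which could leave 147 pairs. That loss comes mainly from the allocation: 147 per group already gives only about 68% at 0.300. It is a separate matter and should not be counted here.

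What remains is that the protocol sources one rate, uses another, and links neither to the endpoint it tests.

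**Conclusion.** The point holds as an internal inconsistency with a modest numerical consequence. The stated 80% power is right at 0.300 and is not met at 34%, the only event rate in section 8.1 with a source. There, 293 and 147 patients give about 77.5%, and 80% needs about 314 and 157.

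This rests on the plan's own margin of 0.13, one-sided 0.025, equal true rates in both groups, independent groups and the unpooled normal approximation. It does not show that the study will fall short. The true composite rate is not given, the sizes are described as minima, and the protocol does not state how many eligible questionnaire respondents exist.

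**What to change.** Rewrite the power paragraph in section 8.1 so that it does three things.

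1. Name the event powered as oral thrush or hoarseness, matching sections 4.2.1 and 8.4.1.
2. Reconcile 34% with 0.300. Either justify 0.300 as the rate of that composite, with its source or reasoning, or use 34%. If 34% is used, restate power as about 77% for 293 and 147, or restate the minimum numbers as about 314 and 157 (about 209 per group at 1:1, labelled as an independent-groups approximation).
3. Show power over assumed composite rates on both sides of 0.30: about 84% at 0.25, 80% at 0.30, 77.5% at 0.34 and 75% at 0.40.

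The cost is one paragraph. Endpoint, margin and analysis are unchanged. If 34% is adopted, the stated power becomes slightly less favourable, or the minimum rises by about 31 records.

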8.3 Matching

Initially, baseline data will be compared between unmatched cohorts. Exact matching for categorical variables and coarsened exact matching for numeric variables will be used to match patients using 1:1 nearest neighbour matching, without replacement. Matching variables such as demographic data, disease co-morbidity and indicators of disease severity will be considered for selection using a combination of baseline data analysis and predictive modelling of the baseline data in relation to the primary outcome variable (independently of treatment group).

If patient numbers allow, patients will be matched on sub groups for age (under 16s and 16-65 year olds) and high/low average ICS dose (1000 µg non-extrafine beclomethasone dipropionate or more/under 1000 µg non-extrafine beclomethasone dipropionate). For the sub-question of step down patients, matching will be implemented if the numbers are sufficient.

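### The minimum sample size in Protocol 8.1 (293 and 147, 80% power) is a 2:1 solution and does not fit the 1:1 matching in 8.3; at that minimum, power is about 68% without within-pair correlation

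*Protocol*

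**What the plan says.** Section 8.1 introduces its figures with "The minimum study numbers are based on the following assumption". The calculation that follows has these parts:

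- Group sizes: "When the sample sizes in the groups are 293 and 147".
- Method: "a two-group large-sample normal approximation test of proportions".
- Error rate and power: "one-sided 0.025 significance level will have 80% power to reject the null hypothesis".
- Margin: a difference that "is 0.130 or farther from zero in the same direction".
- Assumed truth: "assuming that the expected difference in proportions is 0.000" and "the proportion in the standard group is 0.300".

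Section 8.3 combines exact matching on categorical variables with coarsened exact matching on numeric ones, to "match patients using 1:1 nearest neighbour matching, without replacement". Section 8.4.1 analyses the primary questionnaire outcome with a conditional Poisson model, that is, on the matched sets. The protocol describes no 2:1 or variable-ratio matching. It does not say whether 293 and 147 are counts before or after matching, and it makes no allowance for patients who find no match.

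**The concern.** The two sections describe different analysis sets. If 293 and 147 are counts after matching, 1:1 matching cannot produce them. If they are counts before matching, the smaller group limits the set to 147 pairs, and 293 − 147 = 146 or more patients of the larger group drop out.

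This is the protocol's only power statement, and it supports the primary non-inferiority objective in 4.2.1. A team that reached 293 and 147 eligible patients would believe it had 80% power for the planned comparison when it might have clearly less. An inconclusive result on off-licence spacer use could then be given more weight than the data allow.

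**Working it through.** **Inputs, all from 8.1 unless noted.** Proportion 0.30 in both groups (standard 0.300, difference 0.000); margin 0.130; one-sided alpha 0.025 (z = 1.960); power 80% (z = 0.8416); group sizes 293 and 147. The matching ratio of 1:1 is from 8.3.

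**Step 1: reproduce the plan's figure.** With unpooled variance and independent groups,

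power = Φ(margin / SE − 1.960), where SE = √[p(1 − p)(1/n₁ + 1/n₂)].

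For 293 and 147: SE = √[0.21 × (1/293 + 1/147)] = 0.0463. Power = Φ(0.13/0.0463 − 1.960) = 80.1%, which matches the stated 80%. Solving the same formula for a 2:1 ratio returns 147 and 293, so this is the calculation behind 8.1. The alternatives tried do not match: variance taken under the null gives 77.1% or 78.6%, and a two-sided equivalence test gives 60.3%.

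**Step 2: apply the 1:1 ratio at the stated minimum.** With 147 in each arm, SE = √(0.42/147) = 0.0535. Power = Φ(0.13/0.0535 − 1.960) = 68.2%. The chance of missing non-inferiority when the spacers are truly equal is then about 32%, against the intended 20%.

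**Step 3: number of pairs needed for 80%.** n = (1.960 + 0.8416)² × 0.42 / 0.13² = 195.1, so 196 pairs (power 80.2%).

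**Step 4: incomplete matching (assumed match rates, no correlation).** 130 pairs give 62.8%, 120 give 59.4% and 100 give 51.8%. If 80% of the smaller group is matched (0.80 × 147 ≈ 117 pairs), SE = √(0.42/117) = 0.0599 and power is 58.3%.

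**Step 5: within-pair correlation ρ (assumed; the protocol states none).** With SE = √[0.42 × (1 − ρ)/147], power at 147 pairs is:

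| ρ | Power |
|---|---|
| 0 | 68.2% |
| 0.1 | 72.7% |
| 0.2 | 77.6% |
| 0.3 | 82.8% |

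A correlation of about 0.25 would bring 147 pairs back to 80%.

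**Step 6: the other event rate in 8.1.** The section also cites a 34% event rate from the literature. At 0.34, 293 and 147 give 77.5%, 147 pairs give 65.3%, and 80% power needs 209 pairs.

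**The case against.** The numbers in 8.1 are a floor. Section 6.3 describes questionnaire responses from over 55,700 patients with respiratory conditions. How many meet the criteria in 6.1 is not stated, so the actual number of pairs may lie above or below 147, or above or below 196. A reader might infer that the study as a whole has 68% power. The documents do not support that, because the figure applies only to a study that just meets the stated minimum.

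Nor is 68% the power of the model in 8.4.1, which is conditional, adjusts for baseline confounders and reports a rate ratio. It is what the protocol's own two-group formula gives at 147 per arm. Section 8.3 selects matching variables partly by how well they predict the primary outcome, so some positive within-pair correlation is to be expected. Whether it would reach 0.25 is unknown, and losses from exact and coarsened exact matching work in the other direction. These points turn a single figure into a range.

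The study also uses existing records and questionnaires, so 8.1 does not drive recruitment. Low power does not inflate false claims of non-inferiority, and the confidence interval will show the precision achieved.

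One point remains after all this: a stated minimum should secure the stated power under the stated design, and this one does not. The conflict cannot be left to a statistical analysis plan as missing detail, because 8.1 and 8.3 each fix their side explicitly.

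**Conclusion.** The point holds as an internal inconsistency between 8.1 and 8.3. At the stated minimum, 1:1 matching without replacement yields at most 147 pairs. Power on the protocol's own formula is then about 68% rather than 80%, assuming p = 0.30, a true difference of zero, every patient in the smaller group matched, and no within-pair correlation. Relaxing the last two assumptions moves the figure in opposite directions: about 73% to 83% for correlations of 0.1 to 0.3 with full matching, and about 58% for 117 uncorrelated pairs.

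Two stronger readings should be avoided. A reader might call this an arithmetic error, but 80% is right for 293 and 147 independent patients. A reader might also take it as a flaw in the validity of the non-inferiority conclusion. The mismatch affects only the chance of reaching that conclusion; it neither biases the estimate nor raises the type I error.

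**What to change.** Restate the minimum in 8.1 as matched pairs, and say that the count is taken after matching. Either of these would do:

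- Require at least 196 matched pairs for 80% power at p = 0.30. If the 34% rate is the intended assumption, the figure is 209 pairs, so 8.1 should first settle which rate it uses.
- Keep 147 pairs and state power of about 68%, with the no-correlation assumption made explicit.

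Any within-pair correlation relied on to justify fewer pairs should be stated with its source.

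Matching up to 1:2 with a variable ratio is a possible design choice but not a required correction. It reaches the 80% in 8.1 only if 293 and 147 patients remain after matching, so the pool before matching would have to be larger.

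The first two options change wording only and can be made before data extraction. The 196-pair option uses 2 × 196 = 392 patients, fewer than the 293 + 147 = 440 now stated, but the smaller spacer group must supply 196 − 147 = 49 more matched patients. The 147-pair option costs a less favourable stated power.
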